7.2 Primary Statistical Analyses

7.2.1 Primary analyses

To estimate the sensitivity and specificity of each of the methods of detection, the binomial proportion and its 95% confidence interval will be used. Among participants who are HRA positive for HSIL, McNemar's test will be used to compare routine anal cytology with each of the other methods of detection to determine if sensitivity in the diagnosis of HSIL is improved with the other methods. Similarly, among participants who are HRA negative for HSIL, McNemar's test will be used to compare routine anal cytology with each of the other methods of HPV detection to improve specificity. Positive and negative predictive values will be estimated for each method of detection.

The prevalence of HSIL will be estimated as the proportion of women who are HRA positive for HSIL at entry and its 95% confidence interval. Logistic regression analyses will be used to evaluate the association of potential risk factors (cervical HPV, abnormal cervical cytology, behavioral, and immunologic characteristics, such as plasma HIV-1 RNA, current and nadir CD4 count) with diagnosis of HSIL.

To estimate the incidence of HSIL among women who were HRA negative for HSIL at study entry, the Poisson rate and its 95% confidence interval will be estimated from the number of HSIL cases detected divided by the cumulative years of follow-up across these cases. Behavioral risk factors will be assessed by research staff administered surveys at each study visit. Included in these risk factors is the risk of ongoing sexual exposure to HPV in the study population. Logistic regression will be used to evaluate potential risk factors for incidence of HSIL.

To estimate the incidence of anal HPV among women who were negative for anal HPV at study entry, the Poisson rate and its 95% confidence interval will be estimated from the number of anal HPV cases detected divided by the cumulative years of follow-up across these cases. Logistic regression will be used to evaluate potential risk factors for incidence of anal HPV.

Analysis of the results of the Arbor Vita assay will be delayed after the primary analysis is performed using the results of the Hybrid Capture 2 and Aptima Assays, if the Arbor Vita assay is optimized to yield sufficient results from anal cytology specimens in the future.

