[name]
[name]
[contact]
[contact]
Email: [contact]

Operations & Data Management:

AMC Operations & Data Management Center
The EMMES Corporation
[name]
[name]
[contact]
[contact]
Email: [contact]

AMC Biorepository:

[name]
GW Biorepository
George Washington Medical Center
[name]
[name]
[name]
[contact]
[contact]
Email: [contact]

PROTOCOL SYNOPSIS

AMC-084: Screening HIV-Infected Women for Anal Cancer Precursors

| | |
|--------------------------------|--------------------------------------------------------------------------------------------------------------------------------------------------------------------------------------------------------------------------------------------------------------------------------------------------------------------------------------------------------------------------------------------------------------------------------------------------------------------------------------------------------------------------------------------------------------------------------------------------------------------------------------------------------------------------------------------------|
| DESIGN: | Prospective cohort study |
| DURATION: | Up to 2 years |
| SAMPLE SIZE: | 300 |
| POPULATION: | HIV-positive females 18 and older without previously diagnosed high-grade intraepithelial lesions (HSIL) of the anus or anal cancer |
| REGIMEN: | All participants will undergo anal cancer screening with anal cytology and several different anal HPV testing modalities every 6 months for up to 2 years while on study. All participants will undergo High Resolution Anoscopy (HRA) evaluations at baseline/Visit 1, Month 12/Visit 3, and Month 24/Visit 5. Standard screening procedures involving HRA for all abnormal anal cytology tests will also be performed for the interim visits. If diagnosed with HSIL (as defined by HSIL diagnosed on any anal biopsy) at any scheduled study visit, participants will discontinue the study early. |

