4.2.2 On-study evaluations

Evaluations must occur after participant registration. Study visits must be scheduled on the weeks indicated in the Schedule of Evaluations ([Appendix I](#)) from -14 days to +160 days for visits 2-5 for the duration of the participant's participation. For visit 1, all study evaluations should be completed within 50 days before the enrollment visit.

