The novel methods of detection (HPV hybrid capture 2, HPV mRNA assays (APTIMA) and Arbor Vita Onco E6 HPV test) will be evaluated to determine if they improve sensitivity or specificity compared to routine anal cytology using McNemar’s test. With 30 HSIL women, a 20% increase in sensitivity with 25% of participants with discordant results can be detected at the one-sided 0.05 significance level with 78% power. With 270 women negative for HSIL, a 20% increase in specificity with 25% of participants with discordant results can be detected at the one-sided 0.05 significance level with 99% power. Positive and negative predictive values will be assessed for each method of detection.

To determine incidence of HSIL, we will use the information from the women whose initial HRA examination is negative for HSIL. If these women are followed for an average of 1.8 months, we would expect $1.8 \times 270 = 486$ person-years of follow-up. The table below shows the 95% Poisson confidence intervals for two levels of the underlying incidence of HSIL with 486 person-years of observation:

| Underlying incidence of HSIL per 100 person-years | 95% Poisson confidence interval (per 100 person-years) |
|---------------------------------------------------|--------------------------------------------------------|
| 2.06 | (1.11, 3.82) |
| 3.09 | (1.86, 5.12) |

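### Section 7.2.1 divides incident cases by the cases' own follow-up, so as written neither the HSIL nor the anal HPV figure is an incidence rate

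*Combined protocol and SAP*

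**What the plan says.** Objective 2.2.3, one of three primary objectives, is to determine the incidence of anal HSIL and anal HPV over two years. Section 7.2.1 defines the estimators.

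- **HSIL.** The sentence begins "To estimate the incidence of HSIL among women who were HRA negative for HSIL at study entry" and sets the Poisson rate as "the number of HSIL cases detected divided by the cumulative years of follow-up across these cases".
- **Anal HPV.** The sentence begins "To estimate the incidence of anal HPV among women who were negative for anal HPV at study entry" and sets the rate as "the number of anal HPV cases detected divided by the cumulative years of follow-up across these cases".

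Section 7.1 plans the precision of the HSIL rate differently. There, "we will use the information from the women whose initial HRA examination is negative for HSIL", and the person-time is 1.8 × 270 = 486 person-years. A table gives 2.06 (1.11, 3.82) and 3.09 (1.86, 5.12) per 100 person-years. The sentence that introduces the calculation reads "If these women are followed for an average of 1.8 months, we would expect" and then gives the 486 person-years. Section 7.1 has no incidence calculation for anal HPV.

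**The concern.** An incidence rate divides events by the time at risk of everyone who could have had the event. In both sentences of section 7.2.1 the noun that the closing phrase picks up is the detected cases, not the women named at the start. If only the cases' time is counted, the event-free majority drops out of the denominator and the quantity becomes the reciprocal of mean follow-up per case. It carries no information on how many women developed the condition.

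Section 7.2.1 is where the estimator for a primary objective is fixed. HSIL incidence is also on the agenda of the six-monthly reviews in section 8.4, and sections 1.1.10 and 1.1.11 look to this study for inputs to a later cost-effectiveness model. A rate computed by the written rule would be useless for each of these purposes.

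**Working it through.** **Inputs.** From section 7.1: 270 women negative at the initial HRA, mean follow-up 1.8, 486 person-years (PY), and the two table rows. From the schedule: follow-up HRAs for all women at Months 12 and 24. The mean time from entry to detection among cases, *t*, is not given anywhere, so it is assumed and varied.

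**Step 1: reproduce section 7.1.**
- 270 × 1.8 years = 486 PY. Taken as months, 270 × 1.8/12 = 40.5 PY, so the printed unit is wrong and the 486 is right.
- The table does not state case counts. Working back, 10/486 = 2.06 and 15/486 = 3.09 per 100 PY.
- With the log-scale interval, rate × exp(±1.96/√d), d = 10 gives (1.11, 3.82) and d = 15 gives (1.86, 5.12). Both rows match. An exact Poisson interval gives (0.99, 3.78) and (1.73, 5.09), and a plain Wald interval gives (0.78, 3.33) and (1.52, 4.65); neither matches.

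The plan's own table therefore rests on the follow-up of all baseline-negative women.

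**Step 2: apply section 7.2.1 as worded.** With *d* cases and mean case follow-up *t* years, the rate is d/(d × t) = 1/t, or 100/t per 100 PY. The number of cases cancels.

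| Assumed *t* (years) | Written rule, per 100 PY | Ratio to 2.06 | Ratio to 3.09 |
|---|---|---|---|
| 0.5 | 200 | 97.2 | 64.8 |
| 1 | 100 | 48.6 | 32.4 |
| 1.5 | 66.7 | 32.4 | 21.6 |
| 2 | 50 | 24.3 | 16.2 |
| 2.44 | 41.0 | 19.9 | 13.3 |

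The rows for 1 to 2 years span the target months of the scheduled follow-up HRAs. The outer rows are extremes. Detection near month 6 is possible because "Standard screening procedures involving HRA for all abnormal anal cytology tests will also be performed for the interim visits". The value 2.44 years is 24 months plus 160 days, since section 4.2.2 allows visits "from -14 days to +160 days for visits 2-5".

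**Step 3: sensitivity to the number of cases.** At t = 1.5 years:

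| Cases | Written rule, per 100 PY | Cases/486, per 100 PY |
|---|---|---|
| 10 | 66.7 | 2.06 |
| 20 | 66.7 | 4.12 |
| 40 | 66.7 | 8.23 |

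**Step 4: person-time and interval.** The cases' own time runs from 10 × 1 = 10 PY (2.1% of 486) to 15 × 2 = 30 PY (6.2%). With 10 cases at 2 years each, the written rule gives 10/20 = 50 per 100 PY, interval 50 × exp(±1.96/√10) = (26.9, 92.9), against (1.11, 3.82) in the plan's table.

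**Step 5: anal HPV.** The plan gives neither a number at risk nor a planning rate, so no fold error can be stated. As an illustration only, take 30 to 200 women at risk, 5 to 20 cases and 1.8 years of follow-up each. The rate over all women at risk then runs from 5/(200 × 1.8) = 1.4 to 20/(30 × 1.8) = 37.0 per 100 PY. With a mean of 1 year to detection, the written rule gives 100 throughout.

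**The case against.** The best defence is that the intent is plain. Each sentence opens by naming the women negative at entry and asks for a Poisson rate, and section 7.1 shows a worked HSIL denominator that nobody could mistake for case time. An experienced statistician would use all women at risk, so the large ratios describe a literal reading and not a likely result. Design, sample size and data collection are untouched.

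Most of this stands: it is probably a drafting slip, and the ratios rest on assumed detection times. The direct numerical conflict with section 7.1 also concerns HSIL only; for anal HPV the conflict is with the at-risk group named in the same sentence. But naming the group does not change the denominator that the sentence goes on to state. The phrase appears twice, nothing elsewhere corrects it, and for anal HPV no other denominator exists. A primary estimator should not depend on the analyst overriding the plan's words.

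A further objection also stands. Correcting the denominator does not fully define the anal HPV rate, because section 7.2.1 does not say which assay, or combination of assays, decides that a woman is negative at entry or has become a case.

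**Conclusion.** The concern holds, and the text needs correcting before analysis. As worded, both incidence estimators reduce to the reciprocal of mean case follow-up. For HSIL the figure would be 50 to 100 per 100 PY if cases are found on average 1 to 2 years after entry, 16 to 49 times the planning rates; across the extreme detection times of 0.5 and 2.44 years the factor runs from 13 to 97. That the result does not depend on the number of cases needs no assumption. The 1.8 months in section 7.1 is a separate and harmless unit slip: the 486 PY and the table are correct.

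**What to change.** In section 7.2.1, replace the closing three words of both rate definitions with: *across all women negative at study entry (for HSIL or for anal HPV, respectively), each woman's time ending at her first event or at censoring*. In section 7.1, change 1.8 months to 1.8 years. In the same edit it would be sensible to state which assay result defines anal HPV negativity and an incident case.

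The required change is one phrase in two sentences and one unit. It alters no sample size, visit or data item.

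One reasonable convention, not the correction of an error, is to censor event-free women at their last HRA for HSIL and at their last evaluable sample for HPV. If 5% to 20% of the 270 women each lost 0.5 year this way (an assumption), the HSIL loss would be 6.75 to 27 PY, or 1.4% to 5.6% of 486, and 10 cases would give 2.09 to 2.18 instead of 2.06 per 100 PY.

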4.3.3 Nadir CD4+ cell count

The participant's prior nadir CD4+ cell count (absolute value and date) should be documented, when possible, with a copy of the nadir CD4+ cell count report and entered on the CRF. If this documentation is not available, then participant recollection will suffice. For participants who do not know the exact nadir value and for whom there is no source documentation, then recall of the categorical nadir (e.g., < 50, < 100, < 200, 200-500, \geq 500 cells/mm³) will suffice. If unknown, then the category of "unknown" will suffice.

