7.0 STATISTICAL CONSIDERATIONS

7.1 Sample Size

The primary objective of the study is to evaluate the sensitivity and specificity of the following methods for the detection of HSIL of the anus (as determined by consensus pathology): anal cytology, HPV hybrid capture 2, HPV mRNA assays (APTIMA) and Arbor Vita OncoE6 HPV test. Note that throughout this section, HSIL (of the anus) is defined as the local or consensus pathology interpretation of any anal biopsy. At the initial visit, all women will undergo an HRA-directed biopsy to determine if they have HSIL. Since HRA is considered the “gold standard,” the findings on HRA will determine whether a woman is classified as having HSIL or not. HSIL may be under-diagnosed due to operator error, thus the diagnosis of HSIL will be based on the procurement of at least 2 biopsies during HRA. HSIL will be thus be defined as having the diagnosis determined by either local pathologist or the consensus pathology on *any* anal biopsy at a given visit. Based on previous reports,⁴¹ it is anticipated that approximately 10% of women will have HSIL. The prevalence of HRA-proven HSIL can be estimated with a 95% confidence interval of +/- 3.3%.

For each of the methods of detection, the null hypothesis that the sensitivity is 50% can be tested against the alternative that sensitivity is at least 75% at the one-sided 0.05 significance level with power of 0.89 with 30 HSIL participants. The HPV test results from all three tests—APTIMA, HC2, and HPVE6E7—are all dichotomous, i.e., reported as either positive or negative (or unevaluable). With 270 women who are negative for HSIL on HRA, the null hypothesis that specificity is 50% can be tested against the alternative hypothesis that specificity is at least 65% at the one-sided 0.05 significance level with power of 0.99.

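### The plan's two illustrative incidence levels imply only 10 and 15 incident HSIL cases, yet section 7.2.1 assigns an open-ended list of risk factors to logistic regression with no sparse-data method

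*Combined protocol and SAP*

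**What the plan says.** Objective 2.2.3, listed as primary, covers the incidence of anal HSIL and its risk factors over two years. Section 7.2.1 gives the whole method for the risk-factor part in one sentence: "Logistic regression will be used to evaluate potential risk factors for incidence of HSIL". The incident-HSIL text mentions only behavioural factors nearby. The fuller list stands with the prevalent-HSIL model: "cervical HPV, abnormal cervical cytology, behavioral, and immunologic characteristics, such as plasma HIV-1 RNA, current and nadir CD4 count". Hypothesis 2.1.2 names largely the same factors for anal HSIL without separating prevalent from incident disease.

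Section 7.1 bases its specificity calculation on HSIL-negative women ("With 270 women who are negative for HSIL on HRA") and carries the same 270 into the incidence calculation. It then tabulates Poisson intervals "for two levels of the underlying incidence of HSIL with 486 person-years of observation".

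Section 4.3.3 allows nadir CD4 to be recorded loosely: if there is no report and the exact value is not known, "then recall of the categorical nadir" is accepted, and an unknown category is allowed.

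The documents do not say whether the models are univariable or multivariable, how many terms enter, how factors are coded, or what happens if a fit does not converge.

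**The concern.** Maximum-likelihood logistic regression behaves poorly when events are few relative to the terms fitted. If a factor, or one level of a categorical factor, is present in all or none of the cases, its estimate is infinite. Estimates that remain finite are imprecise, and some are far too large.

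The incident-HSIL risk factors belong to a primary objective, and section 1.2 says the study's results should inform screening guidelines. If a fit fails and nothing has been specified, the response (dropping a factor, merging levels, changing method) is chosen after the data are seen.

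This is separate from how follow-up time enters the model.

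**Working it through.** **1. Reproduce the plan's figures.** Inputs from section 7.1: 270 women, mean follow-up 1.8, rates 2.06 and 3.09 per 100 person-years.

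- Person-years: 1.8 × 270 = 486. The unit is printed as months ("If these women are followed for an average of 1.8 months, we would expect"), but only years gives 486. Read as months it would be 1.8/12 × 270 = 40.5 person-years.
- Cases: 2.06 × 4.86 = 10.0 and 3.09 × 4.86 = 15.0.
- Log-scale interval, rate × exp(±1.96/√d):
  - d = 10: rate 10/486 = 2.058 per 100, factor exp(0.620) = 1.859, limits 1.11 and 3.82.
  - d = 15: rate 15/486 = 3.086 per 100, factor exp(0.506) = 1.659, limits 1.86 and 5.12.

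Both printed intervals are matched. Exact Poisson limits, (0.99, 3.78) and (1.73, 5.09), do not match. The table is therefore built on exactly 10 and 15 cases.

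**2. Cases per term.** The list in 7.2.1 has at least six entries: cervical HPV, cervical cytology, behavioural factors, HIV RNA, current CD4 and nadir CD4. As single terms they give 10/6 = 1.7 to 15/6 = 2.5 cases per term.

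**3. Share of maximum-likelihood fits with an infinite estimate.** These are simulations of 270 women, 1,500 to 2,000 data sets per setting. Prevalences, odds ratios (OR) and coding are assumptions, since the plan gives none. The range in the eight-factor row is across repeated simulations of that set-up.

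| Model | 10 cases | 15 cases |
|---|---|---|
| One binary factor, prevalence 40% | 2% | 0.3% |
| One binary factor, prevalence 50%, OR 2 | 4% | 1% |
| Six single-term factors, ORs of 2 for the binary ones | 7% | 1-2% |
| Eight binary factors, prevalence 30-50%, one OR 2.5, rest null | 12-20% | 2-5% |
| One binary factor, prevalence 80%, OR 3 | 46% | 31% |
| Six factors including that one | 56% | 35% |
| Multi-factor model, nadir CD4 in four equal categories | 32% | 11% |
| Multi-factor model, nadir CD4 in six categories | 84% | 57% |

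**4. Size of the estimates.** Eight-factor model, true OR 2.5, maximum likelihood (ML) against Firth; ranges again across repeated simulations.

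| | 10 cases | 15 cases |
|---|---|---|
| Median OR, ML | 2.71 (2.71/2.5 = 1.08) | 2.64 (2.64/2.5 = 1.06) |
| Estimated at about 5 or more, ML | 20-24% | 15-19% |
| Estimated at about 5 or more, Firth | 14% | 10-12% |
| Log-OR root mean squared error, ML | 0.77-0.82 | 0.65-0.67 |
| Log-OR root mean squared error, Firth | 0.70-0.72 | 0.57-0.62 |

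The Firth median at 10 cases was 2.27 in one simulation and 2.48 in another. In the settings of step 3 where Firth was also fitted, every Firth estimate stayed finite.

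**5. Prevalent HSIL.** Section 7.1 anticipates 10% of 300 = 30 cases. In the same eight-factor set-up almost no fits diverged, and an OR above 5 appeared in 5.9% (ML) against 4.3% (Firth).

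**The case against.** The strongest case against is that the failure rates belong to models the plan does not contain. It does not commit to a multivariable model. Common factors fitted one at a time diverge in only about 0.3-4% of data sets. Ordinary maximum likelihood is itself inferred from silence. No power claim or decision rule rests on these odds ratios. An infinite estimate is visible when it occurs, and Firth could be applied then. The basic shortage is information: Firth still puts the true 2.5 above 5 in 14% of data sets at 10 cases. Limiting the terms, exact methods, or labelling the models descriptive would also be defensible.

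Much of this stands, and it rules out several stronger readings that a reader might infer:

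- **That the plan expects 10-15 cases.** It does not say so. The two rates illustrate interval width. Section 8.4 has incidence reviewed every six months and allows sample size and follow-up to be recalculated if prevalence differs substantially, though it does not tie this to the risk-factor models.
- **That fits will often diverge.** This depends on coding and number of terms. At 15 cases with common single-term factors it is uncommon.
- **That odds ratios are exaggerated as a rule.** Median inflation is under 10% in the eight-factor model. With one very common or very strong factor the converged fits are biased downward: a true OR of 8 gave a median of about 6.4-6.9. With a true OR of 2, estimates reaching p<0.05 had medians of about 4.5-6.8, but that is largely selection under power of only about 3-19%.
- **That the prevalent-HSIL models need the same replacement.** The gain at 30 cases is small.

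What does not stand is leaving the choice until a fit fails, because the method would then be chosen with the results in view.

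**Conclusion.** The point holds in limited form. The counts of 10 and 15 follow exactly from the plan's own table, and nothing in the documents protects the incident-HSIL models against sparse events.

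Under ordinary maximum likelihood, infinite odds ratios would arise in about 12-20% of fits at 10 cases and 2-5% at 15 with eight common binary factors. At 10 cases the figure is 30% or more with a very common exposure or categorical nadir CD4. Average inflation is modest. The clearer gain from a penalised fit is fewer large overestimates: about 20% against 14% at 10 cases, and 16% against 11% at 15, for a true OR of 2.5.

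Three assumptions carry this: that unqualified logistic regression means maximum likelihood, that several factors enter together or some are coded in levels, and that the simulated prevalences and odds ratios are reasonable. Single-factor models of common exposures would show little of the problem.

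**What to change.** In section 7.2.1, state that risk factors for incident HSIL will be analysed by Firth penalised-likelihood logistic regression with profile-likelihood confidence intervals. The same penalty applies unchanged if a by-interval binary model is used. Extending it to the prevalent-HSIL models is optional.

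The cost is one sentence and standard software, with no change to data, visits or sample size. The downside is slight shrinkage toward 1. Firth does not replace the information missing from 10-15 events, so wide intervals should still be expected.
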